5.1 Variables

Summary of PK parameters of all participants in the PK set will include pre-dose concentration Ctrough and Cmax on Day 1, Day 28, Day 56 and Day 84. Summary of PK parameters for participants in the PK serial sub-group will include Cmax, Cmin, Tmax, AUClast, AUC0-12h, and T1/2, eff if feasible on Day 1 and Day 28.

5.2 Descriptive analyses

Plasma concentration data for QBW251 will be listed by treatment, subject and sampling time point. Both scheduled and actual times will be included.

Descriptive statistics of QBW251 plasma concentration data will be provided by treatment and visit/sampling time point, including the number and frequency (n, %) of concentrations below the lower limit of quantification (LLOQ), which will be summarized as zero and reported as BLQ in the listing.

Summary statistics of QBW251 plasma concentration data will include mean (arithmetic and geometric), SD, CV (arithmetic and geometric), median, minimum, and maximum. If zero values occur for the values being summarized due to concentrations below the LLOQ, no geometric mean will be calculated.

All PK parameters of QBW251 will be listed by treatment and subject. Summary statistics will be displayed by treatment, using the same summary statistics as for the PK concentrations. An exception to this is Tmax, where only median, minimum and maximum will be presented.

All summaries will be based on the PK analysis set. For all listings displaying individual data, all subjects will be shown, but subjects not in the PK population and values marked as unreliable by the PK Scientist will be flagged.

In addition, the data from this study may be combined with data from other studies and analyzed by means of population modeling and reported separately.

5.3 Statistical model, assumptions and hypotheses

No model-based statistical analysis will be performed for PK.

6 Statistical methods for Pharmacodynamic (PD) parameters

6.1 Primary objective

The primary objective of the study is to assess the change from baseline of QBW251 compared to placebo on the total number of bacteria over all strains at week 12. The PD Analysis Set will be used for analysis of the primary variable.

6.1.1 Variables

The primary variable of the study is the change from baseline in bacterial load as measured by the number of colony forming units (CFU) of potentially pathogenic microorganisms in sputum at week 12. As bacterial load has been found to follow a log-normal distribution, the analysis will be based on log10-transformed scale.

6.1.2 Descriptive analysis

The baseline CFU (on log10-transformed scale) of potentially pathogenic microorganisms in spontaneous sputum is defined as the bacterial load collected at baseline (on log10-transfromed scale). "No growth" means there is no growth from the sputum specimen for that visit. The maximum measurable CFU from lab culture will be set as 600,000,000. Thus, any CFU data that is higher than 600,000,000 will be considered as 600,000,000 in reporting.

In order to be included in the sputum analysis, a subject must provide a sufficient sputum sample at screening, and/or at baseline and at least one post-baseline visit.

Summary statistics will be provided by treatment group and visit for the primary variable and will include mean, standard deviation (SD), coefficient of variation (CV), median, minimum and maximum.

6.1.3 Statistical model, assumptions and hypotheses,

The planned Bayesian repeated measures model will not be performed due to study termination and in absence of informative data, the original PoC criteria will not be evaluated as well.

The primary analysis will include all available data from subjects in the PD analysis set.

Differences between treatment groups (QBW251 versus placebo) for change from baseline in CFU counts (on log10-transformed scale) will be analyzed using a mixed model for repeated measurements (MMRM). The analysis will be carried out using SAS proc mixed procedure with Unstructured covariance structure, with treatment group and visit as fixed effects, baseline log (CFU count), status of macrolides use at screening as covariates, adjusting for effect of treatment*visit, baseline value*visit. Contrasts for treatment differences will be provided together with two-sided 80% confidence intervals.

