# 9.1.5 Early study termination by the sponsor

The study can be terminated by Novartis at any time for any reason. This may include reasons related to the benefit/risk assessment of participating in the study, practical reasons (including slow enrollment), or for regulatory or medical reasons. In taking the decision to terminate, Novartis will always consider the subject welfare and safety. Should early termination be necessary, subjects must be seen as soon as possible and treated as a prematurely withdrawn subject and undergo all assessments of the premature withdrawal visit. The Investigator should ensure contact is made as quickly as possible by telephone and/or e-mail and/or letter. If the study is stopped for a change in the benefit/risk assessment or for medical reasons, patients may be instructed to stop taking the investigational drug QBW251 immediately. Else, patients may be instructed to continue QBW251 intake until they can return to the site for a final assessment. The investigator may be informed of additional procedures to be followed in order to ensure that adequate consideration is given to the protection of the subject's interests. The investigator or sponsor depending on the local regulation will be responsible for informing IRBs/IECs of the early termination of the trial.

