# 12.4.1 Definition of primary endpoint(s)

The primary estimand targets the hypothetical effect as if all patients had stayed on treatment for 12 weeks and as if antibiotics other than macrolide had not been available.

- **Population**: patients are defined by the study inclusion and exclusion criteria. The protocol defines the use of allowed maintenance therapy for this target population, as well as medications that are prohibited.
- Variable: change from baseline in bacterial load as measured by the number of colony forming units (CFU/ml) of potentially pathogenic microorganisms in sputum at week 12. A log10 transformation is applied to the CFU counts before forming the change from baseline computing therefore the log ratio to baseline of the bacterial load.
- **Intervention effect** of interest:
- Intake of antibiotics other than macrolide and intake of rescue medication
- Treatment discontinuation or study participation: hypothetical on treatment CFU counts
  - Summary measure: difference in variable means (QBW251 compared with placebo)

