# 12.4.3 Handling of missing values/censoring/discontinuations

Since the primary estimand is related to an effect outside of antibiotics intake, the CFU counts assessed within 2 weeks after pulmonary exacerbations or during or after last dose of antibiotics, other than macrolide, would not be included in the primary estimand. They will be excluded from the primary estimand, if a valid unscheduled assessment did not happen at the time point for the primary analysis. This is because of the potential confounding effect were expected from the use of antibiotics.

If a valid unscheduled assessment happened at the time point for the primary analysis, then the CFU data collected during the unscheduled visit will be included in the primary estimand. Details about the definition of unscheduled visit is provided in the site manual.

However, the CFU counts at the following visits (if there is no antibiotics use and no pulmonary exacerbation) are assumed not to be confounded and will be included in the primary estimand of interest.

For the primary analysis, only on-treatment data (from date of first randomized dose up to 1 day after date of last randomized dose) will be used as the estimand specifies a hypothetical on treatment effect. Missing on-treatment data related to primary endpoint will not be explicitly imputed. If endpoint measurements are missing at random, an analysis of the available data provides consistent estimates of model parameters.

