6.1.3.1 Handling of missing values/censoring/discontinuations

The CFU counts assessed within 2 weeks after bronchiectasis exacerbations or during or after last dose of antibiotics will not be included in the primary analysis. This is because of the potential confounding effect were expected from the use of antibiotics.

However, the CFU counts at the following visits (if there is no antibiotics use and no bronchiectasis exacerbation) are assumed not to be confounded and will be included in the primary analysis.

Efficacy data collected during intake of rescue medication will be used for analysis, since no confounding effect is expected from the use of rescue medication. Of note, on days of rescue medication intake participants are instructed to fill in the e-diary for that day prior to intake of rescue medication.

Missing on-treatment data related to the primary endpoint will not be explicitly imputed. The repeated measures analysis includes all available information in terms of measurements at all times. If endpoint measurements are missing at random, an analysis of the available data provides consistent estimates of model parameters.

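### The SAP leaves out the protocol's on-treatment window for the primary CFU analysis, so any off-drug values would not be excluded

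*SAP*

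**What the plan says.** Protocol 12.4.1 defines the target: "The primary estimand targets the hypothetical effect as if all patients had stayed on treatment for 12 weeks". Non-macrolide antibiotics are likewise treated as absent. For patients who stop treatment, the strategy is: "Treatment discontinuation or study participation: hypothetical on treatment CFU counts". Protocol 12.4.3 turns this into a data rule, namely that "only on-treatment data (from date of first randomized dose up to 1 day after date of last randomized dose) will be used".

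SAP 6.1.3 replaces the Bayesian model with an MMRM because the study was terminated, and describes the data as follows: "The primary analysis will include all available data from subjects in the PD analysis set." SAP 6.1.3.1, the section on missing values, censoring and discontinuations, contains three relevant statements:

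- An exclusion: "The CFU counts assessed within 2 weeks after bronchiectasis exacerbations or during or after last dose of antibiotics will not be included".
- A statement on imputation: "Missing on-treatment data related to the primary endpoint will not be explicitly imputed."
- A statement on scope: "The repeated measures analysis includes all available information in terms of measurements at all times."

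Neither SAP section gives a time limit relative to the last dose.

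**The concern.** The protocol's estimand concerns what CFU would have been had everyone stayed on drug. Values taken after stopping do not inform that quantity, which is why the protocol removes them. Programmed as written, the SAP would keep them and count them as treated. If the drug works and its effect fades after stopping, the estimated difference is pulled towards zero, and the reported quantity is no longer the one the protocol defines.

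The gap matters more because this MMRM is the only model-based efficacy comparison left. SAP 6.1.4 drops the supplementary analyses and SAP 6.2 drops the modelling of secondary endpoints. No other analysis would show whether off-drug values had moved the result.

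**Working it through.** **1. The two rules side by side**

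| Element | Protocol 12.4.3 | SAP 6.1.3.1 |
|---|---|---|
| Exclude CFU near exacerbations or antibiotics | Yes | Yes (qualifications differ) |
| Keep later visits free of both | Yes | Yes |
| Use on-treatment data only, to 1 day after last dose | Yes | Absent |
| No explicit imputation of missing on-treatment data | Yes | Yes |
| Consistency if data are missing at random | Yes | Yes |
| Measurements at all times are included | No such sentence | Added |

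The SAP attributes several omissions to termination: the Bayesian model, the proof-of-concept criteria, the supportive analyses and the secondary models. The window is not among them.

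The SAP does set time limits elsewhere. Its second section numbered 6.2.1 restricts on-treatment rescue-medication means to values up to the last dose. SAP 7.2 defines an on-treatment period for adverse events, ending 1 week after the last dose. That period could not stand in for the missing one. With the half-life of 10 to 16 hours given in Protocol 4.2, 7 days is 168 hours, or at least 168/16 = 10.5 half-lives.

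**2. Can off-drug CFU values arise?**

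- Protocol 9.1.1 keeps treatment discontinuers in the study unless they withdraw consent, and directs them to the EoS assessments. Table 8-1 shows no sputum culture at EoS.
- Protocol 8.5.2 foresees later visits by patients who stopped treatment but stayed in the study. Table 8-1 schedules sputum culture on Days 28, 56 and 84 and at unscheduled visits.
- Completers who return late for Day 84 sputum stay on study medication (Protocol 3.1), so they remain inside the window.

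Off-drug values are therefore possible, but only when a discontinuer attends a scheduled visit with sputum culture or gives an unscheduled sample.

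**3. The plan's own figure**

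Inputs from Protocol 12.8.1: difference 1.5, SD 2.8, 60 completers (30 per arm), 10% level, 16% drop-out.

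- SE = 2.8 × √(2/30) = 0.723
- Power (one-sided 10%) = Φ(1.5/0.723 − 1.2816) = 78.6%, against the stated 79%
- 60/(1 − 0.16) = 71.4, rounded up to 72, as stated

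The protocol does not state the sidedness. A two-sided 10% test gives 66.6%, so one-sided is the reading that reproduces the figure.

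**4. Size of the attenuation**

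Let f be the share of active-arm week-12 values taken off drug. Assume no residual drug effect in those values. The documents do not give f. Its range here runs from 0 to the planned drop-out rate of 16%, at which every assumed drop-out supplies an off-drug week-12 value. The diluted difference is 1.5 × (1 − f).

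| f | Difference (log10 CFU) | Attenuation |
|---|---|---|
| 0% | 1.50 | 0 |
| 5% | 1.425 | 0.075 |
| 10% | 1.35 | 0.15 |
| 16% | 1.26 | 0.24 |

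**The case against.** The best defence is that nothing in the SAP announces a change. SAP 1.1 says the document implements the protocol's planned analysis. The sentence about all available data is copied from Protocol 12.4.2, where it sits beside the on-treatment limit, and it is not literal even in the SAP, which excludes antibiotic and exacerbation periods. SAP 6.1.3.1 also still speaks of missing on-treatment data. On this view the window is simply inherited.

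Part of this stands: that sentence alone is not the departure. But in the protocol another rule qualifies it, and in the SAP none does. The surviving phrase concerns imputation and excludes nothing. Because this SAP departs from the protocol in several places, a programmer cannot assume that an unstated rule still applies.

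Three stronger readings are tempting, and the documents do not support them.

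- A reader might infer that off-drug values do enter the analysis. The documents show only that they are not excluded.
- A reader might infer that termination itself produced off-drug samples, because Protocol 9.1.5 says "patients may be instructed to stop taking the investigational drug QBW251 immediately". That applies if the study stops for a change in benefit/risk or for medical reasons. Otherwise patients may be told to continue until their final assessment. The documents give no reason for termination and do not show that sputum was cultured afterwards.
- A reader might infer a fall in power from 79% to about 68%. That dilutes the effect as though every drop-out supplied a value while holding the sample at 60. If drop-outs supply values, n per arm is 30/(1 − f). At f = 16% this is 35.7 per arm, with power about 73%; at f = 8% it is 32.6 per arm, with power about 76%. Power is in any case a secondary matter, because SAP 6.1.3 says the proof-of-concept criteria will not be evaluated.

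**Conclusion.** The point holds as an unexplained omission. SAP 6.1.3.1 drops the protocol's on-treatment window, and no other SAP rule removes CFU values taken after the last dose. Any such value would be analysed contrary to the hypothetical on-treatment estimand.

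The consequence is attenuation of the estimated difference, by 0 to 0.24 log10 CFU on a planned 1.5. This rests on two assumptions: no residual effect off drug, and an off-drug share of 0 to 16% of active-arm week-12 values. A residual effect would make the attenuation smaller. The visit schedule suggests the share is small and possibly zero. However, 16% is the planned drop-out rate, and the rate in the terminated study is not given. The SAP itself cites a low sample size in its PK/PD section, so a few values could carry noticeable weight.

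**What to change.** Add to SAP 6.1.3.1 that CFU values taken more than 1 day after the last dose of randomized treatment are excluded from the primary MMRM, citing Protocol 12.4.3. List the excluded values, with counts by arm. If the window was dropped on purpose, say so in the SAP and justify it as a change from the protocol.

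The cost is one sentence, one date filter and one short listing. If no values fall outside the window, the results do not change and the listing documents that.

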
	T
	HRCT assessment on airway structure and function, mucus load
	hsCRP
Pharmacokinetic assessments	Cmax, Tmax, AUClast, AUC0-12h, T1/2, eff when feasible.
Key safety assessments	
 
Physical examinations
 
Vital signs
 
ECG
 
Safety laboratory
 
Adverse events, serious adverse events
 

Other assessments	
 
Bronchiectasis exacerbation
 
PROs: QOL-B, SGRQ, EQ-5D-3L, EXACT-PRO, eDiary
 
Sputum biomarkers: including but not limited to IL-6 and IL-8
 
If feasible, sputum bacterial profile measured by 16s rRNA gene sequencing
 
Serum protein levels measured by SomaScan
 

Data Analysis	The primary endpoint will be analyzed using a Bayesian repeated measures model with change from baseline in CFU as response, adjusting for effect of treatment* visit interaction, status of macrolides use at screening as factor, and baseline CFU counts. In absence of informative data, non-informative priors for the model parameters will be used. The prior for placebo may be updated as a weakly informative prior and will be specified in the statistical analysis plan, should new relevant data become available before the database lock of this study.  • A comparison of QBW251 vs. placebo at week 12 is of primary interest.
Kou worde	Based on the fitted Bayesian model for repeated measures, the posterior probability of QBW251 effect over placebo for log 10 CFU will be calculated. Statistical evidence will be concluded if there is 90% probability that the true effect over placebo for log 10 CFU is >0.  Bronchiectasis, QBW251, colony forming units
Key words	

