## Treatment Period (Day 1 to Day 84):

The treatment period will be 84 days (Day 1 to Day 84), with dosing occurring on Days 1 through 84, and will include a Day 1 Visit, a Day 14 visit (via telephone check), a Day 28 Visit, a Day 56 Visit, and a Day 84 Visit.

On Day 1, after completion of all pre-dose assessments (including the Concomitant medication therapy as per Table 6-2 and Table 6-6), eligible subjects will be randomized in a 1:1 ratio to receive QBW251 300 mg b.i.d. or matching placebo for 84 consecutive days.

At randomization, stratification will be done according to the status of macrolides use and geographic region (sites from China/sites outside China) in order to balance patient distribution

in treatment and placebo group. The first study medication for this treatment period should be administered in the clinic in the morning of Day 1, following the pre-dose pharmacokinetic blood sample collection as indicated in the Assessment Schedule (NOTE: all PK sampling times are relative to the first dose of the treatment day).

During treatment period, subjects will return to the site for scheduled visits for biomarker blood/sputum sample collections, PK, safety and efficacy assessments including completion of the questionnaires. On visit days, subjects will take their morning dose in the clinic after completion of pre-dose assessments.

On scheduled sputum collection visits, sputum specimens are recommended to be collected in the morning at pre-dose time point and if possible before breakfast. In case subjects can't produce enough sputum on the individual scheduled visits, they can come back to site up to 3 days after the scheduled visit to try to produce a sputum sample. If spontaneous sputum collection attempts are still not satisfactory, investigator may take decision to collect sputum sample after induction by the inhalation of saline.

At Day 14, site will call the subject to evaluate the compliance and to check patient well-being.

Pharmacokinetic blood sampling (pre-dose and 3hr post dose) will be done at Day 1, Day 28, Day 56 and Day 84 visits. Additionally, although serial PK sampling is optional, efforts will be made to have a subset of approximately 30-40 subjects undergo serial PK sampling at pre- and up to 8 hours post-dose on Day 1 and Day 28.

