### 6.3.2 Treatment assignment, randomization

Upon signing the informed consent form, the subject will be assigned the next sequential number by the investigator. The investigator or his/her staff will contact the IRT and provide the requested identifying information for the subject to register them into the IRT.

At Day 1, all eligible patients will be randomized via Interactive Response Technology (IRT) to one of the treatment arms.

The investigator or his/her delegate will contact the IRT after confirming that the patient fulfills all the inclusion/exclusion criteria. The IRT will assign a randomization number to the patient, which will be used to link the patient to a treatment arm and will specify a unique medication number for the first package of investigational treatment to be dispensed to the patient. The randomization number will not be communicated to the caller but will be used by the IRT system. The patient will retain the Subject Number throughout the study as the unique identifier. If the subject fails to be treated for any reason, the IRT should be notified within 2 days that the subject was not treated, and the reason will be entered into the CRF.

The randomization numbers will be generated using the following procedure to ensure that treatment assignment is unbiased and concealed from subjects and investigator staff. A subject randomization list will be produced by the IRT provider using a validated system that automates the random assignment of subject numbers to randomization numbers. These randomization numbers are linked to the different treatment arms, which in turn are linked to medication numbers. A separate medication list will be produced by or under the responsibility of Novartis Global Clinical Supply (GCS) using a validated system that automates the random assignment of medication numbers to packs containing the study treatment.

The randomization scheme for subjects will be reviewed and approved by a member of the Randomization Office.

Follow the details outlined in the SOM regarding the process and timing of treatment assignment and randomization of subjects.

Randomization will be stratified by macrolides use status and geographic region (from China/not from China).

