#### 12.4.2 Statistical model, hypothesis, and method of analysis

The primary analysis will include all available data from subjects in the PD analysis set.

The CFU counts assessed within 2 weeks after pulmonary exacerbations or during or after last dose of antibiotics other than macrolide would be set to missing if a valid unscheduled assessment did not happen at that time point for the primary analysis.

The primary endpoint will be analyzed using a Bayesian repeated measures model with change from baseline in CFU counts (on log10-transformed scale) as response, including the fixed factors and covariates but are not limited to: treatment group, visit, effect of treatment\*visit interaction, status of macrolides use at screening, and baseline CFU counts (on log10-transformed scale) by time interaction. In absence of informative data, non-informative priors for the model parameters will be used. The prior for placebo may be updated as a weakly informative prior and will be specified in the statistical analysis plan, should new relevant data become available before the database lock of this study.

A comparison of QBW251 vs. placebo is of primary interest. Based on the fitted Bayesian model for repeated measures, the posterior probability of QBW251 effect over placebo for  $log_{10}CFU$  will be calculated. Statistical evidence will be concluded if there is 90% probability that the true effect over placebo for  $log_{10}CFU$  is >0.

The posterior probabilities of efficacy will be assessed according to the following criteria:

1. **Go / success criteria** at final: Better than placebo with high confidence (at least 90% probability that the change from baseline in  $log_{10}CFU$  for QBW251 is better than placebo, i.e. Posterior Prob (delta > 0) > 0.90)

Due to the nonconfirmatory nature of this study, no multiplicity adjustment will be applied.

In addition, the mean and corresponding two-sided 80% credible interval for the QBW251 difference to placebo from the posterior distribution will be presented.

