6.1.4 Supportive analysis

The planned supportive/supplementary analysis will not be performed due to study termination.

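### The primary MMRM adjusts for macrolide use but omits region, the other stratification factor; if region is prognostic, the 80% interval is slightly conservative (minor)

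*SAP*

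**What the plan says.** Protocol 6.3.2 names two stratification factors: "Randomization will be stratified by macrolides use status and geographic region (from China/not from China". Section 3.1 (Treatment Period) says the same, "At randomization, stratification will be done according to the status of macrolides use and geographic region (sites from China/sites outside China", and gives balance between the arms as the purpose.

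SAP 6.1.3 replaces the planned Bayesian model with an MMRM with unstructured covariance, "with treatment group and visit as fixed effects, baseline log (CFU count), status of macrolides use at screening as covariates", plus treatment-by-visit and baseline-by-visit interactions. Region is not in the model, and the SAP does not mention the regional stratification anywhere. The output is specified as follows: "Contrasts for treatment differences will be provided together with two-sided 80% confidence intervals".

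The protocol's own model descriptions do not name region either. The summary (Data Analysis) lists treatment by visit, "status of macrolides use at screening as factor, and baseline CFU counts", as a closed list. Section 12.4.2 leaves its list open: "including the fixed factors and covariates but are not limited to".

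The rest of the planned inference on this endpoint was withdrawn on termination. SAP 6.1.3 says that "the original PoC criteria will not be evaluated as well". SAP 6.1.4 says: "The planned supportive/supplementary analysis will not be performed due to study termination". The SAP's PK/PD section refers to a low sample size but gives no number.

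**The concern.** Stratifying on region makes the arms nearly equal in regional mix, so a regional difference in outcome adds little to the true sampling variance of the treatment contrast. A model without region does not know this. It counts the regional variation as residual noise, and the model-based standard error comes out larger than it should. The usual practice is to analyse with the factors used to randomise. Here one of the two is in the model and the other is not, with no reason given.

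What is at stake is narrow. With secondary modelling also dropped (SAP 6.2), the MMRM contrast is the one model-based treatment comparison left on the primary endpoint, and its 80% interval is the statement of precision that readers will use. The issue is how exact that interval is, not whether the estimate is right.

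**Working it through.** **Inputs from the documents** (protocol 12.8.1): SD of change 2.8 log10; assumed treatment effect 1.5 log10; 60 completers, so 30 per arm; 72 randomised; 16% drop-out; 10% significance level. SAP 6.1.3: two-sided 80% interval.

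**Inputs that are assumptions.** The documents do not give China's share of patients (p), the regional difference in mean change (d) or the final sample size.

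**Step 1: the plan's own figures.** SE = 2.8 × √(2/30) = 0.723. Power = Φ(1.5/0.723 − 1.2816) = Φ(0.793) = 78.6%, which reproduces the stated 79% with a one-sided 10% test (a two-sided test gives 66.6%). Drop-out: 60/(1 − 0.16) = 71.4, rounded up to 72, as stated. The 80% half-width at the planned size is 1.2816 × 0.723 = 0.927 log10.

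**Step 2: effect of omitting region.** The share of variance due to region is R² = p(1 − p)d²/2.8². With allocation balanced on region, the SE without region is too large by the factor 1/√(1 − R²), and the nominal 80% interval covers 2Φ(1.2816/√(1 − R²)) − 1. For example, with p = 0.5 and d = 1, R² = 0.25/7.84 = 0.032, so the factor is 1.016 and coverage is 80.7%.

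| d (log10) | SE excess, p = 0.25 | SE excess, p = 0.50 | Coverage |
|---|---|---|---|
| 0.5 | 0.3% | 0.4% | 80.1–80.2% |
| 1.0 | 1.2% | 1.6% | 80.5–80.7% |
| 1.5 | 2.8% | 3.8% | 81.2–81.7% |

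A simulated week-12 ANCOVA (72 randomised in blocks of 4 within strata, one-sixth lost, p = 0.4, d = 1.5; 8,000 runs) agrees. Coverage was 81.4% without region and 80.0% with it; mean width was 1.896 and 1.832.

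**Step 3: net effect of adding region.** The extra term costs a degree of freedom, and small strata are imperfectly balanced. The table gives the change in mean 80% interval width over several simulations: single-visit ANCOVA with baseline and macrolide use, with stratified blocks and losses of 0–40%; and a three-visit unstructured MMRM without missing data. China's share was varied from 20% to 50%.

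| Patients randomised (assumed) | d = 0 | d = 1 log10 |
|---|---|---|
| 14 | +1.2 to +4.1% | 0.0 to +2.0% |
| 20 | +0.8 to +1.9% | −1.4 to +0.4% |
| 40 | 0.0 to +0.8% | −1.8 to −0.4% |
| 60 | +0.1 to +0.5% | −1.9 to −0.8% |

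At 20 randomised with 16% loss and d = 1.5, adding region narrowed the mean width from 3.898 to 3.831, that is by 1.7%.

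**The case against.** The strongest objection is that the proposed term may not help this trial. The SAP itself describes the sample as low. At 14 patients region tends to widen the interval even with a 1 log10 regional difference, and at 20 it is about neutral. The model is already heavy. With sputum load at Days 28, 56 and 84 it has 10 fixed-effect parameters (intercept, treatment, 2 visit, 2 treatment-by-visit, baseline, 2 baseline-by-visit, macrolide) and 6 covariance parameters. This stands, and it is why the point is minor. The final number is not given, so a net gain can be neither shown nor ruled out.

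A second objection also stands: the documents do not show that region is prognostic. A reader might infer it from protocol 12.8.1, which allows for higher variability in either region and for an imbalance between Europe and China. That passage concerns variance and recruitment, not mean change, and a main effect does not address unequal variances.

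Third, the calculation uses the unadjusted SD. The MMRM already removes variation due to baseline load and macrolide use, so what matters is the regional difference and the SD left after those terms. That could move the figures either way.

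Three stronger readings are tempting but not supported:

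- **Bias or inflated error.** Under stratified allocation the estimate is unbiased and the interval errs towards being too wide.
- **A compromised proof-of-concept decision.** The criteria are no longer evaluated.
- **A SAP that departs from the protocol.** The protocol's own models name macrolide use and not region, so the SAP carries the omission over.

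**Conclusion.** The point holds as a small, conservative loss of precision and as a cheap improvement. It is not an error that affects a conclusion. If regions differ by 0.5 to 1.5 log10 in mean change and China contributes 25–50% of patients, the SE is 0.3–3.8% too large and the nominal 80% interval covers 80.1–81.7%. If regions do not differ, nothing is lost by the omission.

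Besides the assumed regional difference and share, this rests on the protocol's SD of 2.8, on regional balance being largely kept among the patients analysed, and on missingness not depending on region given the model.

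**What to change.** In SAP 6.1.3, add region (China / outside China) to the MMRM as a one-degree-of-freedom fixed main effect alongside macrolide use. Fix the exception in advance so that it does not depend on results: drop region only if one region contributes no patients, or patients from only one arm, to the analysis. Protocol 12.4.2 leaves room for the term. The protocol summary's list is closed, so record region in the SAP as an addition to that list.

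The work is one line of SAP text and one model term, using a factor already used to randomise. The statistical cost, if region has no effect, is an 80% interval wider by under 1% at 40–60 patients, about 1–2% at 20 and about 2–4% at 14. At about 20 or fewer, a net gain needs a regional difference above about 1 log10. In simulation with a 20% China share, the rule drops region in 30–35% of trials of 14 and 13–16% of trials of 20, but in at most 1% at 40–60.

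A sentence giving a reason for leaving region out would document the choice but would not change the interval, so it does not replace this fix.
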